Title: Prospective, multicenter, single-arm phase II clinical trial for biomarker validation in patients with advanced and / or metastatic colorectal cancer with KRAS gene not mutated treated with chemotherapy plus biweekly cetuximab as first-line therapy.

Study Phase: Phase II

Indication:

Advanced and / or metastatic colorectal cancer (CCRA)

Principal Objective:

Validation of the biomarkers BRAF, IGF1P / MMP7 (DP) and PI3K-PTEN to predict PFS in patients with advanced and / or metastatic colorectal cancer with non-mutated KRAS treated with standard chemotherapy plus biweekly cetuximab as first-line therapy.

Secondary Objectives:

Secondary biological markers (MMP-7, IGF-1 and IGFBP3) will be analyzed in serum and tumor tissue to predict acquired resistance.

OS based on proposed classification

Objective response according to RECIST 1.1 (*E.J. Cancer 2009; 228-47*)

Safety of administration of cetuximab 500 mg / m² every 2 weeks.

Clinical Hypothesis:

Our hypothesis is that the proposed markers will make it possible to select those patients who will benefit the most from biweekly cetuximab treatment.

Study design:

Single-arm prospective phase II clinical trial.

Prior to inclusion in the trial and to confirm eligibility, the investigator or designee will review the status of KRAS, BRAF, IGF1P / MMP7 (DP) and PI3K-PTEN, existing radiological images in addition to any other relevant clinical documents (reports, notes, etc.) to confirm that the subject has previously untreated advanced and / or metastatic colorectal cancer.

FOLFIRI (m) / FOLFOX6 (m) will be administered once every 2 weeks until 6 months of treatment, disease progression (PE), or unacceptable toxicity. Cetuximab will be administered every 2 weeks until disease progression. If patients do not show progression after 6 months of treatment with FOLFIRI (m) and FOLFOX6 (m), they will continue to receive biweekly cetuximab as monotherapy until progression.

Subjects who stop receiving FOLFOX6 (m) / FOLFIRI (m), for example due to toxicity, may receive biweekly cetuximab as monotherapy until disease progression. Following discontinuation of biweekly cetuximab, the treatment period will end and subjects will attend a follow-up safety visit

Single-arm, multicenter, prospective phase II clinical trial for biomarker validation in patients with advanced and / or metastatic colorectal cancer with non-mutated KRAS gene treated with chemotherapy plus biweekly cetuximab as first-line therapy

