30 ± 3 days later.

Throughout the trial, subjects will undergo tumor response assessment (using the revised [RECIST 1.1] Solid Tumor Response Assessment Criteria) every 12 weeks (three months) until disease progression. In subjects with symptoms that indicate disease progression, tumor response should be assessed at the time of symptoms.

Biologic study

K-RAS, in patients who do not have a determination, and other markers of tumor tissue will be measured at the Navarra University Clinic (CUN) and the markers of the blood samples will be measured at the Hospital Clínic de Barcelona (HCB).

Biomarkers will be measured prior to patient enrollment. In addition, blood samples will be collected every 3 months until disease progression.

Endpoints:

Principal endpoint:

The main endpoint is progression-free survival comparing two cohorts, which will be defined according to the classification based on the predictive capacity of the response of the biomarkers.

Secondary endpoint:

Secondary biological markers in serum and tumor tissue will be analyzed to predict acquired resistance.

OS based on proposed classification

Objective response according to RECIST 1.1 (*E.J. Cancer 2009; 228-47*) (objective response rate)

Response duration

Safety (Type, frequency and intensity of appearance of Adverse Events)

Single-arm, multicenter, prospective phase II clinical trial for biomarker validation in patients with advanced and / or metastatic colorectal cancer with non-mutated KRAS gene treated with chemotherapy plus biweekly cetuximab as first-line therapy

Sample size:

A sample size of 170 patients will be needed.

Principal Inclusion Criteria:

Patients, men or women aged 18 years or older, with advanced and / or metastatic colorectal cancer with non-mutated KRAS, histologically or cytologically confirmed and radiologically evaluable, ECOG performance status of 0 to 2 with adequate hematological, renal and hepatic function and informed consent signed.

Ver listado completo de Criterios de Inclusión en el apartado 6.1 del protocolo

Principal Exclusion Criteria:

Patients who have received prior systemic treatment for metastatic colorectal carcinoma will be excluded from the trial. Patients with previous surgery for metastases (liver, lung or other), metastases in the central nervous system or with significant cardiovascular disease will also be excluded.

Ver listado completo de Criterios de Exclusión en el apartado 6.2 del protocolo

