5. EXPERIMENTAL PLAN

5.1 Study Design

Single-arm, multicenter, and prospective phase II clinical trial for validation of biomarkers in patients with advanced and / or metastatic colorectal cancer with non-mutated KRAS gene treated with chemotherapy plus biweekly cetuximab as first-line therapy. Patients with non-mutated CCRAyM and KRAS will be eligible.

Patients will be recruited over a 24-month period.

Before inclusion in the study and to confirm eligibility, the investigator or designee will send a sample of the primary tumor to the CUN, which will centrally review the status of KRAS (if the patient already has a prior determination of the status of the KRAS gene, it can be included in the assay without the need to re-determine K-RAS). At the same time, the investigator or designee will review existing radiological images in addition to any other relevant clinical documents (reports, notes, etc.) to confirm that the subject has previously untreated advanced and / or metastatic colorectal cancer.

The proposed biomarkers will be measured at the beginning of the study. Investigators can treat patients with CCRAyM and non-mutated KRAS with biweekly FOLFOX6 (m) or FOLFIRI (m) + cetuximab. Other investigative agents will be excluded.

FOLFIRI (m) / FOLFOX6 (m) will be administered once every 2 weeks until 6 months of treatment, disease progression (PE), or unacceptable toxicity. Cetuximab will be administered every 2 weeks as stipulated in this protocol until disease progression. If patients do not show progression after 6 months of treatment with FOLFIRI (m) and FOLFOX6 (m), they will continue to receive biweekly cetuximab as monotherapy until progression.

Subjects who stop receiving FOLFOX6 (m) / FOLFIRI (m), for example due to toxicity, may receive biweekly cetuximab as monotherapy until disease progression. Following discontinuation of biweekly cetuximab, the treatment period will end and subjects will attend a follow-up safety visit 30 ± 3 days later.

Throughout the trial, subjects will be assessed for tumor response using Response Assessment Criteria for Solid Tumors (RECIST 1.1). The tumor response of the subjects will be evaluated by CT (helical or conventional) thoracic and abdominal performed in the baseline phase and every 12 weeks (three months) until the progression of the disease. In subjects with symptoms that indicate disease progression, tumor response should be assessed at the time of symptoms.

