6.1 Inclusion criteria

Male or female \geq 18 years old.

Able to understand, sign and date an informed consent form approved by the CEIC.

Advanced and / or metastatic colorectal cancer confirmed histologically or cytologically by the investigator.

KRAS non-mutated colorectal cancer.

At least 1 unidimensionally measurable lesion $>$ 10 mm with helical CT or $>$ 20 mm with conventional CT according to the revised RECIST 1.1 criteria. (All disease sites should be evaluated \leq 28 days before the start of treatment).

Patients with the following characteristics will be included:

1. Recurrence after adjuvant treatment +/- radiotherapy with a disease-free interval $>$ 6 months after completion.

2. De novo diagnosis of the disease.

ECOG (Eastern Cooperative Oncology Group) performance status of 0, 1 or 2. (recommended only 0-1)

Life expectancy \geq 3 months.

Adequate bone marrow function: neutrophils $\geq 1.5 \times 10^9 / L$; platelets $\geq 100 \times 10^9 / L$; hemoglobin $\geq 9 \text{ g / dL}$.

Liver, kidney and metabolic functions as follows:

Adequate liver function: ASAT (SGOT) and ALAT (SGPT) $2.5 \times \text{ULN}$ ($5 \times \text{ULN}$ if there are liver metastases). Total bilirubin $< 1.5 \times \text{ULN}$. Alkaline phosphatase $2.5 \times \text{ULN}$ ($5 \times \text{ULN}$ in case of liver metastases or $10 \times \text{ULN}$ in case of bone metastases).

Renal function, calculated as creatinine clearance or creatinine clearance for 24 hours $\geq 50 \text{ mL / min}$.

Magnesium $\geq \text{ULN}$, calcium $\geq \text{ULN}$.

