6.4 Treatment assignment

The selection of treatment between FOLFOX-6 (m) + biweekly cetuximab or FOLFIRI (m) + biweekly cetuximab will be made by the Principal Investigator, according to the usual clinical practice of his center.

Single-arm, multicenter, prospective phase II clinical trial for biomarker validation in patients with advanced and / or metastatic colorectal cancer with non-mutated KRAS gene treated with chemotherapy plus biweekly cetuximab as first-line therapy

After confirmation of eligibility, the center's staff will fax an inclusion request form to the Sponsor (GEMCAD Technical Secretariat [REDACTED]) in which they must record the treatment chosen by the Principal Investigator for the patient.

The GEMCAD Technical Secretariat will return a communication to the center to confirm that a new patient has been registered in the study.

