10.3 General considerations

The primary endpoint and secondary efficacy endpoints will be analyzed using the ITT analysis group and the per-protocol analysis group.

Efficacy analyzes will be based on radiographic images collected during the study and analyzed by the investigator. Any examination that the investigator classifies as not evaluable will be omitted from the analysis (it will be considered as no examination).

For continuous variables, the mean, standard error (for efficacy variables) or standard deviation (for other measurements), median, 25th percentile, 75th percentile, minimum, and maximum will be provided. For discontinuous data, the frequency and percentage distributions will be provided. The two-sided 95% confidence intervals of the Kaplan-Meier quartiles will be calculated using the methods described by Brookmeyer and Crowley (Brookmeyer, 1982). Two-sided 95% confidence intervals for the Kaplan-Meier rates at specific time points will be calculated using the methods described by Collett (Collett, 1992).

Safety data will be analyzed throughout the study.

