- h. If thoracic CT scan at selection did not show any chest abnormality, chest X-ray imaging were performed in subsequent evaluations. A CT scan was performed to confirm any abnormality identified upon chest X-ray imaging performed after selection, and all subsequent evaluations were thoracic CT imaging.
- i. Response evaluation was conducted according to the revised RECIST 1.1 criteria, every 12±1 weeks until PD. Subject follow-up was performed regardless of discontinuation or a delay in treatment.
- j. ECOG PS evaluation (on day 1 of each treatment cycle).
- k. Tumour evaluation and serum CEA test was performed every 12 weeks and at the follow-up visit only in subjects who have withdrawn from the trial for reasons different from PD, and in those who have not had a serum CEA test in the previous 12 weeks.
- l. Paraffin embedded tumour block was sent to the central laboratory (Fundación Jiménez Díaz) at selection. The centralised evaluation laboratory perform a tumour block quality assessment. It was compulsory that KRAS and NRAS mutational status (wtKRAS and NRAS) was confirmed by a validated laboratory before the inclusion of any subject.
- m. Follow-up of all subjects who permanently discontinued the treatment before disease progression (e.g. due to unacceptable toxicities) was conducted to evaluate PFS (i.e., tumour imaging) every 12± 1 week until PD or until the end of study (unless the reason for study discontinuation was total consent withdrawal). After PD, all subjects underwent a follow-up assessment of disease status, subsequent cancer therapy, and survival assessment every 12 ± 1 weeks until the end of study (maximum of 24 months).
- n. Blood samples for biomarker analysis were withdrawn before the study treatment initiation and every 12 weeks ± 1 weeks until PD.

Table 3: SDV schedule

Form	Variables
Eligibility	Pathology report, staging, prior treatment.
Demographics	Date of birth, ECOG PS, ICF (signature, date, and completion)
Primary tumour	Diagnosis date, location, staging and surgery
Adjuvant or neoadjuvant treatment	Yes/No
KRAS/NRAS	Central reviewing
Baseline biochemistry and SAE biochemistry	LDH, creatinine, bilirubin, and CEA
Baseline haematology and SAE haematology	Haemoglobin, platelets, and leukocytes

Metastasis	Nº affected organs and hepatic M1 (number and size)
CT scans or MRI	All variables (date, lesions measure, location, new lesions) and RECIST criteria
AEs	Grade and need of SAE communication

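### The protocol synopsis has the investigator review BRAF, DP and PI3K-PTEN before inclusion although only KRAS decides eligibility, which leaves the marker-related comparison of investigator-read PFS open to bias

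*Protocol*

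**What the plan says.** The protocol gives two accounts of the molecular review before inclusion.

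- Synopsis, Study design: as part of confirming eligibility, "the investigator or designee will review the status of KRAS, BRAF, IGF1P / MMP7 (DP) and PI3K-PTEN", together with images and clinical documents.
- Section 5.1: the investigator "will send a sample of the primary tumor to the CUN, which will centrally review the status of KRAS". The other markers are not part of this review; they are measured at the start of the study.

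The only molecular inclusion criterion in section 6.1 is "KRAS non-mutated colorectal cancer", and no exclusion criterion in 6.2 uses BRAF, DP (IGF-1Rp/MMP-7 double positivity) or PI3K-PTEN. In the SAP, a footnote to the schedule (Table 2) reads: "It was compulsory that KRAS and NRAS mutational status (wtKRAS and NRAS) was confirmed by a validated laboratory before the inclusion of any subject".

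On timing, the synopsis states "Biomarkers will be measured prior to patient enrollment", and section 5.1 repeats it. On who acts and who reads:

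- The choice between FOLFOX and FOLFIRI "will be made by the Principal Investigator, according to the usual clinical practice of his center" (Protocol 6.4).
- The investigator's own decision is a listed reason for stopping treatment (Protocol 5.1.1 and 8.3).
- Symptoms suggesting progression trigger an assessment outside the 12-week schedule (Protocol 5.1 and the section on tumor response evaluation).
- "Efficacy analyzes will be based on radiographic images collected during the study and analyzed by the investigator" (Protocol 10.3). The SAP synopsis and SAP 6.5.1.4 also rely on the investigator's assessment, and neither document plans an independent read.

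**The concern.** The trial has one arm, so what it learns about the markers comes from comparing patients who differ in marker status. If the person who manages the patient and reads the scans has seen that status, the marker can affect the recorded outcome by routes other than biology. These are the decision to enrol, the regimen, the threshold for an unscheduled scan, the call of progression, the call that a scan is not evaluable (which drops it from the analysis under Protocol 10.3), and discretionary stopping.

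The investigator would also have expectations. Protocol 4.4 reports worse outcomes with DP, with BRAF mutation in some studies, and with PTEN loss. An apparent gain in predicting PFS could then partly reflect management and reading. Nothing is gained in return, because three of the four results reviewed play no part in eligibility.

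**Working it through.** The plan gives no figure for this point, so the check is mainly of text.

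**Step 1. Is the review needed for eligibility?** Protocol 6.1 needs KRAS, and 6.2 needs no marker. Protocol 8.1 lists all the markers to be assessed on the samples but singles out KRAS for determination before enrolment. The SAP needs KRAS, NRAS and adequate sample quality. BRAF, DP and PI3K-PTEN are needed nowhere, so the synopsis conflicts with the body of the protocol.

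**Step 2. Is there a masking statement?** None was found. The markers are measured centrally before enrolment, and neither document says that results are kept from sites or readers.

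**Step 3. Where is the endpoint sensitive?** SAP 6.5.1.1 and 6.5.1.5 use PFS at 12 months as a yes/no outcome. Scans fall every 12 weeks: 4 × 12 = week 48 and 5 × 12 = week 60. Twelve months, about week 52, lies between them. A progression that would be seen first at week 60 changes the 12-month status if it is called at week 48, or on a symptom-triggered scan before week 52. Shifts far from month 12 do not.

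**Step 4. How much does one patient weigh?** Group sizes are from SAP Table 6.

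| Group | n | One patient's 12-month status (1/n) |
|---|---|---|
| Mutant BRAF | 20 | 5.0 points |
| DP | 23 | 4.3 points |
| Mutant PI3K or PTEN ≤3 | 98 | 1.0 point |
| Wild-type PI3K and PTEN >3 | 69 | 1.4 points |

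**Step 5. Illustration on assumed inputs.** None of these inputs is an estimate from the trial: a marker with no true effect, 155 patients, median PFS 12 months, scans every 12 weeks, follow-up uniform over 4 to 28 months (about 83 to 85 events), 1,500 runs (standard error about 0.006). Progression is called one visit early in a share of marker-positive patients. The table gives the two-sided log-rank type I error.

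| Share called early | 40% marker-positive | 11% marker-positive |
|---|---|---|
| 0% | 0.047 | 0.048 |
| 10% | 0.054 | 0.063 |
| 20% | 0.063 | 0.068 |
| 30% | 0.075 | 0.062 |
| 50% | 0.082 | 0.082 |

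The 11% is 20/181, the mutant-BRAF share. The uneven middle of that column is within simulation error. The inflation is modest unless early calling is common, and its direction is built into the assumption.

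**Step 6. How far can the synopsis step have been carried out?** SAP 6.5.2 reports that about 70 of the first 157 patients (70/157 = 45%) had samples insufficient for biomarker analysis. The review cannot have been completed for everyone. The documents do not say for whom it was.

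**The case against.** The strongest reply is that one synopsis sentence is being read as the operating plan. Protocol 5.1, 6.1 and 8.1 and the SAP all point to KRAS or RAS only. Measuring markers centrally before enrolment does not mean returning the results to sites. The shortage of usable samples was noticed only after 157 patients had been recruited, which is hard to square with investigators reviewing every marker at inclusion. There are also safeguards: RECIST 1.1 on a 12-week schedule, regimen set by centre practice, therapy among the adjustment variables in SAP 6.5.1.5, source verification of scan data (SAP Table 3), and limits on elective surgery (Protocol 7.5).

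Much of this stands as a limit on the point. It does not remove it. The synopsis is part of the protocol, the conflict is real, and no sentence settles it in favour of masking. Source verification confirms what was recorded; it does not replace the reader. Control for regimen is also unsettled, since the SAP synopsis leaves treatment out of the score while SAP 6.5.1.5 counts it among the four clinical factors.

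Three stronger readings are tempting, and the documents do not support them.

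- *That the only contrast in the trial is unblinded.* Protocol 10.2 and 10.4 compare two cohorts from a classification built later from clinical variables and markers, and the SAP compares AUCs of scores with and without each marker. An investigator cannot know a patient's final class at inclusion.
- *That every route favours the hypothesis.* Not enrolling the worst marker-positive patients would weaken a marker effect. Starting second-line treatment without documented progression is censored under Protocol 10.2.1, and follow-up for PFS continues after treatment stops. Expectations for PFS are mixed too: Protocol 4.4 cites one trial with no BRAF association with PFS and only a trend for DP.
- *That four mutant-BRAF patients (4/20 = 20 points) could produce the whole planned difference.* The 20-point target was set for a 40/60 split by the combined classification, not for a single-marker group of 20.

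**Conclusion.** The point holds as a weakness of the plan. Followed as written, the synopsis shows three study markers to the person who manages the patient and alone reads progression. It does so for an eligibility purpose that these markers do not serve, and no statement elsewhere keeps the results from sites. The marker-related comparison of PFS is therefore open to assessment and management bias.

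The documents do not establish that bias occurred, how large it would be or which way it would go. The 5.0 and 4.3 points per patient show how fragile the BRAF and DP groups are; PI3K-PTEN is much less fragile. The conclusion rests on reading the synopsis literally and on the absence of any masking statement. It should be fixed because the change is cheap. It is not evidence against the trial's results.

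**What to change.** 1. In the synopsis, delete BRAF, IGF-1Rp/MMP-7 and PI3K-PTEN from the pre-inclusion review, so that it matches Protocol 5.1 and 6.1.
2. State that the central laboratories release only KRAS/RAS status to sites and hold the three study markers until database lock. Any marker result that a site requests locally is recorded with its date.
3. In the report, state for how many patients a study marker was known at the site at inclusion. Use inclusion as the reference point because it is a baseline fact. Whether a marker was known before progression depends on how long the patient stayed progression-free, and selecting on that would bring in its own bias.
4. If markers were known at inclusion for some patients but not all, repeat the primary analysis as a sensitivity analysis in those whose markers were not known.

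The SAP already describes recruitment in the past tense, so for this trial items 3 and 4 are the ones that can still inform the reader.

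The cost is wording in the protocol and laboratory instructions, plus one line of data per patient. No extra test, visit or reader is needed. The downsides are small: a site that wants BRAF must request it locally and record that it did so, and the sensitivity analysis has fewer patients and less precision.

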3. GENERAL INFORMATION

3.1 Clinical Trial Identification

Protocol Code: GEMCAD-1002

Title: Single-arm, multicenter, prospective phase II clinical trial for biomarker validation in patients with advanced and / or metastatic colorectal cancer with non-mutated KRAS gene treated with chemotherapy plus biweekly cetuximab as first-line therapy.

N EudraCT: 2010-019236-12

3.2 Clinical Trial Type

Single-arm prospective phase II clinical trial.

3.3 Description of the Products under Study

FOLFOX6 (m)

Oxaliplatin 5 mg / ml powder for solution for infusion.

Leucovorin (CALCIUM FOLINATE). Powder for solution for injection (350 mg of folinic acid).

Fluorouracil (5-FU) solution for injection 50 mg / ml.

FOLFIRI (m)

Irinotecan 20 mg / ml (irinotecan hydrochloride trihydrate) concentrate for solution for infusion (equivalent to 17.33 mg / ml irinotecan).

Leucovorin (CALCIUM FOLINATE). Powder for solution for injection (350 mg of folinic acid).

Fluorouracil (5-FU) solution for injection 50 mg / ml.

CETUXIMAB

[figure not shown]
Cetuximab (Erbitux®) 2 mg / ml solution for infusion

